### **6.3 Inclusion Criteria**

Subjects who meet the following criteria may be included in the study:

1. Age 18 to 85 years;
2. Diagnosis of acute ischemic stroke with mechanical thrombectomy procedure < 8 hours from onset of symptoms or last known well;
3. Large Vessel Occlusion on CT scan or MRI in the Anterior Cerebral Vasculature up to A1, M1, M2, or Posterior Cerebral Vasculature;
4. ASPECTS 6 – 10 or volume of diffusion restriction < 50 mL;
5. Use of the Q Aspiration Catheter as the first line treatment according to the IFU;
6. Signed informed consent by patient or legally authorized representative.

### **6.4 Exclusion Criteria**

Subjects who meet any one of these criteria will be excluded from the study:

1. Occlusions in multiple vascular territories (e.g., bilateral anterior circulation, or anterior/posterior circulation) extracranial occlusion or tandem occlusion;
2. Evidence of dissection in the carotid or target artery for treatment;
3. Evidence of recent/fresh haemorrhage on presentation;
4. Unwilling to agree to a 3-month follow up visit.

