## **7.2 Subject Information and Consent**

Subjects must be informed about the study prior to enrollment. Only those subject's (or subject's legal representative) who voluntarily provide written consent will be allowed to participate in the study. The original signed consent form should be retained in the patient's study records and a copy should be provided to the patient or legal representative. If the patient is unable to provide informed consent or is deceased prior to consenting, a legally authorized representative may consent to use the patient's medical record.

A sample informed consent document suitable for use in this study will be provided. Iterations of this document must be approved by the reviewing Ethics Committee and the sponsor or sponsor-designate. Subjects must be presented with the most current EC approved version of the consent form for signature and study enrollment. The consent form and consent discussion should be in a language the subject understands. No study related data may be collected prior to patient consent. Study subject's must be consented prior to or at the study 3 month visit.

Subjects may withdraw participation at any time during the investigation without sacrificing their rights as a patient or compromising their quality of medical care.

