# **8 STUDY PROCEDURES**

## **8.1 Screening and Enrollment**

All patients diagnosed with acute ischemic stroke who undergo mechanical thrombectomy with the Q Aspiration Catheter as first line therapy, without regard to gender, are eligible for screening to participate in the clinical study. Patients will be screened based on the study inclusion and exclusion criteria after the procedure.

A screening log should be kept of all subjects in whom the Q Aspiration Catheter was used to prevent bias in subject selection. Death may be added to the screening log as reason for screen failure, if applicable.

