**TABLE 3 DATA COLLECTION**

Assessment	Baseline	Procedure	Post Procedure	Day 7 or Prior to Discharge	3 Month Follow-up
Visit Window	< 8 hours from stroke onset	< 8 hours from stroke onset	0 - 36 hours post procedure	1 day prior or day of discharge/transfer or Day 7	90 - 120 days post-procedure
Informed Consent			X 	X 	X 
Medical History	X				
Vitals	X				
Neuroimaging (CT/MRI)	X		X		
NIHSS	X		X		
mRS	X				X

Procedure and device use data		X			
Serious Adverse Event Collection		X	X	X	X

1 Informed Consent may happen at any time after the procedure but must happen prior to the initiation of the 3 month visit (but may be signed at the beginning of the visit)

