## **10.2 Statistical Methods**

This study is a single arm, registry study with endpoints compared to well defined and published outcomes. This study is designed for observational data to be collected and reported. There will be no formal statistical hypothesis testing conducted, and therefore sample size is not based on power calculations.

Data analysis will comprise of descriptive statistics (means, standard deviations, rates, correlations, etc.) on the variables detailed in the study endpoints and other data collected.

The analyzed population will consist of all subjects who signed an informed consent form.

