### Secondary Endpoints

- Successful revascularization defined as mTICI 2b-3 with the Q Aspiration Catheter as determined by an independent Angiographic Core Lab.
- Embolization to a new neurovascular territory during the procedure as determined by the Core Lab
- Good functional outcome measured by Modified Rankin Score of 0-2 at 90 days
- All-cause mortality at 90 days

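### The dissection exclusion, and less clearly the multi-territory occlusion exclusion, has no time point but is applied after the procedure, so a procedural complication can exclude the patient who had it

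*Combined protocol and SAP*

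**What the plan says.** Eligibility is decided with the procedure already finished. Section 8.1 states: "Patients will be screened based on the study inclusion and exclusion criteria after the procedure". Section 6.4 makes each of its four exclusions mandatory. The third is dated: "Evidence of recent/fresh haemorrhage on presentation". The first two are not: "Occlusions in multiple vascular territories (e.g., bilateral anterior circulation, or anterior/posterior circulation) extracranial occlusion or tandem occlusion" and "Evidence of dissection in the carotid or target artery for treatment". The synopsis gives them no time point either.

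The same kinds of finding appear on the outcome side. Section 13.2 lists as a secondary endpoint "Embolization to a new neurovascular territory during the procedure as determined by the Core Lab". Section 8.3 collects new-territory embolization and also procedure- and device-related adverse events, which is where a procedural dissection would be recorded. Dissection is not itself a named endpoint.

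Four provisions decide what happens to a patient who is screened out:

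- The footnote to Table 3: "Informed Consent may happen at any time after the procedure but must happen prior to the initiation of the 3 month visit".
- Section 7.2: "No study related data may be collected prior to patient consent".
- Section 8.3: the angiogram goes to the core lab only once the subject has consented.
- Section 10.2: "The analyzed population will consist of all subjects who signed an informed consent form".

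Section 8.1 also asks for a screening log covering every patient in whom the catheter was used, with the declared aim of guarding against biased selection.

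**The concern.** A site that applies these criteria afterwards already has the whole procedural angiogram. If the guide catheter or the Q Catheter dissected the carotid, that patient now shows evidence of carotid dissection, and exclusion 2 as worded removes them. A fragment that lodged in another territory raises a similar, weaker question under exclusion 1. The complication would then act as a reason for leaving the patient out of the study that is meant to count it.

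The study aims to demonstrate safety and performance (Section 4.1), its endpoints are to be set against published outcomes (Section 10.2), and Section 5.3 says there are no clinical investigation data so far. With at most 50 subjects, a few lost events would visibly change a complication rate.

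**Working it through.** **1. Is a baseline time point implied?** Exclusion 3 is dated and exclusions 1 and 2 are not, so a reader cannot safely supply the date. Nor is eligibility purely pre-procedural elsewhere. Inclusion 5 requires use according to the IFU, which depends on how the procedure went, and Section 8.1 allows death to be entered as a reason for screen failure.

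**2. Which events fit the wording?**

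| Event caused by the procedure | Criterion | Fit | Where it would be counted |
|---|---|---|---|
| Carotid or target-artery dissection | Exclusion 2 | Literal | Adverse events (8.3) |
| Embolus to a new territory | Exclusion 1 | Arguable | Secondary endpoint (4.3, 13.2) |
| New intracranial haemorrhage | Exclusion 3 | None; limited to presentation | Primary safety endpoint |

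**3. When is the event lost?** If the patient is screened out before consent, no study data may be collected, no film goes to the core lab, and the patient is outside the analysis set. If the patient consents and is later found ineligible, Section 10.2 taken literally keeps them. The order of screening and consent is not stated. The loss therefore arises mainly when exclusion comes before consent, and consent can come as late as the 3-month visit.

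**4. How large could the effect be?** The plan states no event rates and no power calculation, so there is no figure to reproduce. The rates below are assumptions. With true complication rate p and share f of complication cases excluded, the observed rate is p(1 − f)/(1 − pf).

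| Assumed p | f = 0 | f = 0.5 | f = 1 |
|---|---|---|---|
| 2% | 2.0% | 0.01/0.99 = 1.0% | 0% |
| 5% | 5.0% | 0.025/0.975 = 2.6% | 0% |
| 10% | 10.0% | 0.05/0.95 = 5.3% | 0% |

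In counts, take 50 otherwise eligible patients with 4 events: 4/50 = 8.0%. Excluding 1, 2 or all 4 of the cases gives 3/49 = 6.1%, 2/48 = 4.2% or 0/46 = 0%.

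If enrolment still reached 50 and no event was seen, the exact two-sided 95% upper limit would be 1 − 0.025^(1/50) = 7.1%. An assumed true rate of 10% would lie above it.

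**5. Final mTICI.** Assume 42/50 = 84.0% true success and remove 4 patients. If 3 of them were failures, the result is 41/46 = 89.1%. If all 4 were successes, it is 38/46 = 82.6%. The sign depends wholly on that assumption.

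**6. Symptomatic haemorrhage.** Neither undated exclusion refers to it, so its rate changes through this route only if an excluded patient also had such a haemorrhage.

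**The case against.** The best reply is that a baseline finding is plainly meant. Exclusion 1 groups multi-territory occlusion with extracranial and tandem occlusion, which describe the presenting lesion, and inclusion 3 defines the occlusion from CT or MRI. Reading exclusion 1 to remove new-territory emboli would empty the protocol's own endpoint, and its examples do not name spread within one hemisphere, such as from the middle to the anterior cerebral artery on the same side. This largely stands, and it makes the embolus half the weaker one. It does less for dissection: the reference to the artery for treatment says which vessel is meant, not when the dissection appeared.

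Safeguards also exist. The screening log makes exclusions visible, the analysis set has no eligibility condition beyond consent, and Section 9.2 sends serious events attributable to the device through post-market reporting. These reduce the loss. However, nothing requires the log to record complications of excluded patients or to be reported with the results, and none of these provisions puts a lost event back into the study's rates.

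A reader might go further and infer that the bias favours the device throughout, final mTICI included. The documents do not support this. Success is defined in the target vessel, so an embolus elsewhere is not by definition a failure, and step 5 shows that either direction is possible. Nor do they support saying that the safety results as a whole are compromised, because the primary safety endpoint is symptomatic haemorrhage and its matching exclusion is already dated.

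**Conclusion.** The point holds, with dissection the stronger half. As written, a procedure-induced dissection meets a mandatory exclusion, and a new-territory embolus arguably meets another. If the exclusion precedes consent, the event leaves the adverse event results or the embolization endpoint. The bias in those rates can only be downward. Its size cannot be stated: the figures above rest on assumed rates and an assumed share of cases excluded, and nothing shows that sites would read the criteria this way.

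This is a descriptive study without hypothesis testing, so no formal conclusion is invalidated. It is a change that should be made rather than one on which the study stands or falls. It goes beyond a missing detail because a site following the text faithfully would produce the bias.

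**What to change.** In Section 6.4 and the synopsis, limit exclusions 1 and 2 to findings present before treatment, as shown on baseline imaging or on the initial diagnostic angiographic run of the target circulation. Add that a dissection or new-territory occlusion attributed to the procedure is an adverse event or outcome and not a reason for exclusion.

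The anchor should not be placement of the guide catheter. Section 8.3 expects diagnostic angiography to verify the occlusion but does not say that it precedes guide placement, so a dissection already present and first seen through the guide would be misclassified as a complication. The attribution clause covers the reverse case, a dissection caused during access and visible on the first run.

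Report screening-log exclusions by reason alongside the results.

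The cost is a sentence or two in two places and one extra table. No new imaging is needed, since baseline imaging and diagnostic angiography are already expected. The downside is that reported complication rates may be slightly less favourable. The change is best made before enrolment, because data on an excluded, unconsented patient may not be recoverable.

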## **7 ETHICS**

### **7.1 Ethics Committee (EC) and Ethical Conduct of the Study**

This study will be conducted in compliance Good Clinical Practice and the ethical principles of the Declaration of Helsinki. The study protocol and consent must be approved by the responsible EC for each investigational site. Study activities (patient consent) must not commence prior to receipt of documentation of EC approval by the site and sponsor. Copies of the Investigator's reports and the EC continuance of approval must be sent to the sponsor. The Investigator and study staff must comply with the requirements of their EC.

The Investigator must submit and, where necessary, obtain approval from the EC for all subsequent protocol amendments and changes to the Informed Consent Form. The Investigator must notify the EC of deviations from the protocol, SAEs, and SADEs occurring at the site in accordance with local procedures.

## **7.2 Subject Information and Consent**

Subjects must be informed about the study prior to enrollment. Only those subject's (or subject's legal representative) who voluntarily provide written consent will be allowed to participate in the study. The original signed consent form should be retained in the patient's study records and a copy should be provided to the patient or legal representative. If the patient is unable to provide informed consent or is deceased prior to consenting, a legally authorized representative may consent to use the patient's medical record.

A sample informed consent document suitable for use in this study will be provided. Iterations of this document must be approved by the reviewing Ethics Committee and the sponsor or sponsor-designate. Subjects must be presented with the most current EC approved version of the consent form for signature and study enrollment. The consent form and consent discussion should be in a language the subject understands. No study related data may be collected prior to patient consent. Study subject's must be consented prior to or at the study 3 month visit.

Subjects may withdraw participation at any time during the investigation without sacrificing their rights as a patient or compromising their quality of medical care.

# **8 STUDY PROCEDURES**

## **8.1 Screening and Enrollment**

All patients diagnosed with acute ischemic stroke who undergo mechanical thrombectomy with the Q Aspiration Catheter as first line therapy, without regard to gender, are eligible for screening to participate in the clinical study. Patients will be screened based on the study inclusion and exclusion criteria after the procedure.

A screening log should be kept of all subjects in whom the Q Aspiration Catheter was used to prevent bias in subject selection. Death may be added to the screening log as reason for screen failure, if applicable.

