## **6 STUDY POPULATION**

### **6.1 Study Population**

The observational study population is patients diagnosed with large vessel occlusion acute ischemic stroke within 8 hours of stroke onset treated with mechanical aspiration thrombectomy with the Q Aspiration Catheter as first line therapy. The Q Aspiration Catheter must be used according to the IFU to be included in the study. All study candidates (or legal representative) must be able to provide written informed consent and agree to be followed at 3 months post-procedure.

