## **8.3 Mechanical Thrombectomy Procedure**

To be eligible to participate, the procedure had to begin within 8 hours of stroke onset with planned first line therapy of the use of the Q Aspiration Catheter alone.

Digital subtraction angiography should have been undertaken to verify vessel occlusion using diagnostic angiography and contrast agent. Repeat diagnostic angiography should have been done on the treated region to assess recanalization grade per mTICI criteria after Q Catheter use and at the end of the procedure.

The Q Aspiration Catheter must be used per the Instructions for Use to be eligible for participation. Per the IFU, the Q Aspiration Catheter may be used with three aspiration attempts.

Procedural data collection will include:

- General procedural data (anesthesia use, procedure start time, revascularization time and end time, thrombolytic therapy administered, ancillary device use)
- Target vessel location
- Pre-and post-procedure target vessel flow information
- Q Aspiration Catheter use during the procedure
- Rescue device use, if applicable
- Treatment outcome
- Embolization to a new territory
- Procedure and device-related adverse events or any device related problems
- De-identified procedural angiogram should be collected for the Core Lab (only after subject consent) (see Section 11.7)

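### Early deaths and other non-enrolled uses of the Q catheter can drop out of the denominator unseen, because section 10 never reports the screening log

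*Combined protocol and SAP*

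**What the plan says.** **Timing of screening.** Section 8.1: "Patients will be screened based on the study inclusion and exclusion criteria after the procedure". Section 8.3 adds: "Repeat diagnostic angiography should have been done on the treated region to assess recanalization grade per mTICI criteria", both after Q use and at the end of the procedure.

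**Timing of consent.** The footnote to Table 3 allows consent at any point from the procedure to the start of the 3-month visit, whose window is 90 to 120 days.

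**Deaths before consent.** Section 7.2 lets a legally authorized representative consent to use of the record of a patient who has died. Section 8.1 offers another route: "Death may be added to the screening log as reason for screen failure, if applicable".

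**IFU condition.** Sections 6.1, 6.3 and 8.3 all require use according to the IFU; section 8.3 puts it as "The Q Aspiration Catheter must be used per the Instructions for Use to be eligible for participation". That section also mentions three aspiration attempts as part of the IFU.

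**Safeguard.** Section 8.1: "A screening log should be kept of all subjects in whom the Q Aspiration Catheter was used to prevent bias in subject selection".

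**Analysis.** Section 10.2 defines the analysed population as everyone who signed consent, plans descriptive statistics on the endpoints and other data collected, and compares this single arm with published outcomes. Sections 10.1 to 10.3 do not mention the log.

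**The concern.** Whether a patient enters the denominator is settled after the angiographic result is visible at the site, and in some cases after the patient has died. The protocol recognises the risk and names a remedy, but the analysis plan never uses it. No count of Q uses, table of reasons or patient flow is planned.

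The most exposed endpoints are 90-day mortality and mRS 0-2. A death logged as a screen failure is absent from both, although it is a mortality event and a failure on mRS 0-2. The revascularization rates could be affected if patients left out for other reasons did worse. With no control arm, the rates are read against published figures, so a reader needs to know how many Q uses lie outside a denominator of at most 50 (section 6.2), and why.

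**Working it through.** **1. The route out of the denominator.** Take a patient treated with the Q catheter who dies before anyone has signed consent.
- Under section 7.2 a representative may consent. The patient then enters the set defined in section 10.2 and counts as a death.
- Under section 8.1 the death may be logged as a screen failure. The patient is then outside that set and does not count.

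Both routes are permitted, and no rule chooses between them. The same patient can therefore add a death to the 90-day rate or leave no trace in any planned output.

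**2. Is the log reported anywhere?** Section 10.1 restates the purpose and primary endpoints. Section 10.2 gives the descriptive methods and the analysed population. Section 10.3 covers summary statistics and missing data. None mentions the log, and sections 12.1 to 12.3 do not list it among the records. The general reference in section 10.2 to other data collected would permit a report but does not commit to one.

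**3. Size.** There is no plan figure to reproduce: 50 is a cap, and section 10.2 says it does not rest on a power calculation. The documents give neither outcome rates nor the number of non-enrolled Q uses. What follows assumes 50 enrolled, 8 deaths among them, and d logged deaths by day 90 that were not enrolled.

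Mortality with those deaths added = (8 + d)/(50 + d). The mRS 0-2 proportion is multiplied by 50/(50 + d), whatever its value, because d is added to the denominator only.

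| d | 90-day mortality | Multiplier for mRS 0-2 |
|---|---|---|
| 0 | 8/50 = 16.0% | 1.000 |
| 2 | 10/52 = 19.2% | 50/52 = 0.962 |
| 5 | 13/55 = 23.6% | 50/55 = 0.909 |
| 10 | 18/60 = 30.0% | 50/60 = 0.833 |

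The exact 95% interval for 8/50 is 7.2% to 29.1%. The results for d = 2 and d = 5 fall inside it; d = 10 falls above it.

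**4. Revascularization.** Here the outcomes of non-enrolled patients are unknown, so only extremes can be given. With x successes in 50 and k patients left out, the rate lies between x/(50 + k) and (x + k)/(50 + k), a width of k/(50 + k). For an assumed 45/50 (90.0%; exact 95% interval 78.2% to 96.7%):
- k = 2: 45/52 = 86.5% to 47/52 = 90.4%
- k = 5: 45/55 = 81.8% to 50/55 = 90.9%
- k = 10: 45/60 = 75.0% to 55/60 = 91.7%

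Only k = 10 has a lower extreme below the interval.

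**5. Wording of first-line use.** Section 8.3 makes eligible a procedure "with planned first line therapy of the use of the Q Aspiration Catheter alone", which is an intention. Section 6.3 asks for "Use of the Q Aspiration Catheter as the first line treatment according to the IFU", which is conduct. The two can classify the same case differently.

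**The case against.** The strongest reply is that this is a descriptive registry with no hypothesis test, that the log covers every Q use, and that it can be reported under the general wording of section 10.2. Deaths need not be lost, because a representative may consent. All of this is true. It shows that selection could be disclosed, not that the plan requires it.

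Several stronger readings are tempting, and the documents do not support them.
- *The IFU condition removes difficult cases.* The IFU is not in the text. Section 8.3 says the catheter may be used with three aspiration attempts, but the wording is permissive and does not establish a limit.
- *Q-alone failures are dropped.* Sections 8.3 and 13.3 provide for rescue use to be recorded, so IFU-conforming failures that go on to rescue stay in.
- *The main set is IFU-conforming.* Section 10.2 analyses all consented subjects, so one later found to be off-IFU remains.
- *Reasons for non-enrolment are optional.* In section 8.1 the permissive verb concerns death only. The sentence presupposes that the log holds reasons; it does not say that every reason must be recorded.
- *Bounds on mTICI are essential.* Choosing which non-enrolled patients were otherwise eligible may need baseline data that sections 7.2 and 8.2 restrict to consented patients. The bounds also rest on extreme assumptions.

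**Conclusion.** The point holds as an omission in the analysis plan. Followed as written, sections 8.1 and 10.2 allow early deaths and other non-enrolled Q uses to leave a denominator of at most 50 with nothing reported to show it. The effect on 90-day mortality and mRS 0-2 has a known direction: each eligible 90-day death left out makes both look better. For revascularization the direction depends on outcomes the log does not hold.

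The size is unknown and may be zero. Under the assumed 8 deaths in 50, 5 logged deaths would raise mortality by 23.6 - 16.0 = 7.6 points. A reader might infer that selection has occurred or is intended; the text shows only that it could occur and would not be visible. This should be corrected before the rates are set beside published ones.

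**What to change.** 1. **Section 8.1:** require the log to record every Q use and the reason for each non-enrolment: death (and whether by day 90), off-IFU use, no consent, not approached, the cap of twenty per centre (section 6.2), and each failed criterion.
2. **Section 10:** add a flow table by site of all logged Q uses, enrolled and not enrolled by reason. Use counts only, subject to ethics committee agreement given the consent rule in section 7.2.
3. **Sections 7.2 and 8.1:** reconcile the two routes for a death before consent. In section 10, also report 90-day mortality and mRS 0-2 with logged pre-consent deaths by day 90 added to the denominator, as deaths and as not mRS 0-2, where the log gives no other reason for non-enrolment.
4. **Sections 8.3 and 6.3:** reconcile planned first-line use with actual use, so that sites classify cases alike.

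Keep all consented subjects as the main set. All-fail and all-succeed bounds on mTICI are optional, and only where the log alone identifies the patients.

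The cost is slightly more logging at the sites, one added table, an amendment submitted to the ethics committee (section 7.1), and possibly less favourable reported rates. Treatment and the main analysis do not change.

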#### 8.5 3 Month Follow Up

The final and only study-specific visit will be the 3 month (90 - 120 days) office or telephone visit. The Modified Rankin Scale (mRS) is administered, a review of the subject's health and assessment for serious adverse events will be recorded.

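### Sites that follow the plan may include or omit the same otherwise eligible patient who dies before consent, so 90-day mortality can depend on who was asked, and the screening log has no planned use that would show it

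*Combined protocol and SAP*

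**What the plan says.** Section 8.1 sets the timing: "Patients will be screened based on the study inclusion and exclusion criteria after the procedure". The footnote to Table 3 fixes the consent window: "Informed Consent may happen at any time after the procedure but must happen prior to the initiation of the 3 month visit". Section 7.2 agrees that subjects "must be consented prior to or at the study 3 month visit". That visit may fall as late as day 120, because section 8.5 states: "The final and only study-specific visit will be the 3 month (90 - 120 days) office or telephone visit". The whole 90-day mortality period can therefore pass before anyone is asked for consent.

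Two provisions cover a patient who dies before consent. Section 7.2 says that if the patient "is deceased prior to consenting, a legally authorized representative may consent to use the patient's medical record". Section 8.1 says "Death may be added to the screening log as reason for screen failure, if applicable".

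Inclusion criterion 6 in section 6.3 accepts a representative's signature. Section 6.1 asks candidates or their representatives to agree to follow-up at 3 months and does not say how this applies to someone already dead. Section 7.2 adds: "No study related data may be collected prior to patient consent". Section 10.2 restricts the analysed population to subjects with a signed consent form and says that endpoints will be compared with published outcomes. Sections 4.3 and 13.2 list 90-day mortality and mRS 0-2 as secondary endpoints.

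Section 8.1 also provides a safeguard: "A screening log should be kept of all subjects in whom the Q Aspiration Catheter was used to prevent bias in subject selection". Sections 10.1 to 10.3 plan no count, table or analysis from that log.

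**The concern.** Both provisions for a death before consent are permissions, and the plan does not rank them. A site that asks the family and obtains consent adds the death to the numerator and denominator of the mortality rate. A site that records a screen failure removes it from both. Entry to the analysis can therefore depend on the outcome being measured.

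Section 10.2 sets the endpoints against published results. A mortality rate whose denominator may depend on survival is hard to compare with a published series, with or without a hypothesis test. Without log counts, a reader of the final report could not tell whether any deaths were left out, or whether survivors were left out as well.

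**Working it through.** **Plan's own figure.** There is none to reproduce. The plan gives no expected mortality, benchmark or consent rate, and section 10.2 says that the sample size of up to 50 is not power-based. Every rate below is an assumption used to show the mechanism.

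**Route of an eligible patient who dies before consent.**
- Representative asked and consents (7.2, 6.3): enrolled and analysed.
- Representative not asked, death logged as screen failure (8.1): no data (7.2), not analysed (10.2).
- Neither route breaches the plan, and no section says which comes first.

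**Effect on reported mortality.** Let m be true 90-day mortality among patients eligible apart from consent, p the share of deaths lost and q the share of survivors lost. Then

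reported = m(1−p) / [m(1−p) + (1−m)(1−q)].

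In odds form, reported odds = true odds × (1−p)/(1−q). The reported rate is below m only if p > q, equals m if p = q, and is above m if p < q.

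With m = 15% (assumed):
- p = 25%, q = 0: 0.1125/0.9625 = 11.7%.
- p = 50%, q = 0: 0.075/0.925 = 8.1%.
- p = 25%, q = 25%: 0.1125/0.75 = 15.0%, unchanged.
- p = 25%, q = 40%: 0.1125/0.6225 = 18.1%, too high.

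**Would the loss be visible?** In the second case, 50 enrolled subjects come from 50/0.925 = 54 otherwise eligible patients, with about 4 deaths counted and 4 left out. The exact 95% interval for 4/50 is 2.2% to 19.2%. It contains both 8% and 15%, so the reported rate alone would not reveal the loss.

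**Does adding back the logged deaths repair it?** If only deaths are added back, the rate becomes m / [m + (1−m)(1−q)]. This equals m when q = 0 and exceeds m otherwise:
- p = 25%, q = 25%: 15.0% becomes 0.15/0.7875 = 19.0%.
- p = 25%, q = 40%: 18.1% becomes 0.15/0.66 = 22.7%.

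Both results are further from the assumed true 15% than the unadjusted rate. If all eligible unconsented patients of known vital status are added back, dead and alive, the rate returns to m when vital status is complete. The repair therefore needs counts of unconsented survivors as well as deaths.

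**The case against.** The strongest reply is that the plan already covers these deaths. Section 7.2 names the deceased patient and allows representative consent, and section 6.3 accepts that signature. The qualifier at the end of the death sentence in 8.1 can be read as limiting it to cases where no representative consent was obtained. The log covers every use of the catheter, so such deaths can be seen. Much of this stands. Loss of deaths is not automatic, and a subject consented by a representative belongs in the analysed population. The silence of 10.2 on representatives is a matter of wording and does not exclude anyone. What the reply does not supply is a duty to ask, or any reporting of the log.

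A second reply is that no section requires sites to approach every survivor either. That also stands, and it is why the direction of any bias is open.

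A third reply is that the study is descriptive, has at most 50 subjects and tests no hypothesis. This lowers the weight of the point but does not remove it, because 10.2 still plans a comparison with published outcomes. The expectation of little missing data in 10.3 does not help, since it concerns the primary endpoints in subjects already in the analysis population.

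A reader might infer that the plan excludes deaths before consent by rule, or that reported mortality will be too low. The documents support neither. The first is contradicted by 7.2. The second needs deaths to be lost at a higher rate than survivors, which nothing in the plan establishes.

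**Conclusion.** The gap is real and can be shown from the text: a stated rule lets compliant sites select on the outcome, and the log meant to guard against this is not used. Confidence is high for the gap and does not extend to direction or size. The figures of 11.7% and 8.1% against a true 15% assume that no survivors are lost. With survivors also lost, the same true rate can read 15.0% or 18.1%.

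A reader might also infer that mRS 0-2 must read high and symptomatic haemorrhage low. The mRS result follows if deaths are lost and no survivors are; otherwise it depends on which survivors are missing. For symptomatic haemorrhage, whose definition in 13.2 includes bleeds leading to death, the direction depends on how fatality among those patients compares with overall mortality and on who else is lost. The documents settle neither.

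This should be fixed, at the lower end of that grade, because the study is descriptive and mortality and mRS are secondary.

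**What to change.** 1. **Consent and log rules.** Amend 7.2 and 8.1 so that sites approach all consecutive patients treated first line with the Q catheter who are eligible apart from consent. For each such patient who dies before consenting, sites seek representative consent and document the attempt, where the ethics committee allows. State in 6.1 that the agreement to 3-month follow-up does not apply to a patient already deceased. Keep death as a log entry in every case where it occurs before consent, with a sub-reason if the patient is not enrolled: representative declined, none found, or approach not permitted.

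2. **Report the log in mutually exclusive categories.** Treated first line with the Q catheter; not eligible; eligible and enrolled; eligible and not enrolled. Split the last group by vital status at day 90 (dead, alive, unknown) and by reason (not approached, declined, no representative found, approach not permitted). The day-90 split matters because consent may come as late as day 120, and a death after day 90 is not a 90-day death. Use aggregate counts only, with ethics committee agreement: classifying unconsented patients needs some record review, and 7.2 bars study data before consent.

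3. **Add one supporting analysis to 10.2.** If the counts are permitted, show 90-day mortality with all eligible unconsented patients of known vital status in the denominator and those dead by day 90 also in the numerator. If only deaths can be counted, label the result an upper scenario for mortality and say that it overshoots when survivors are also unconsented.

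**Cost.** A small amendment, site effort to contact representatives, possible ethics committee agreement, one extra table, and rates that may look less favourable. The log and the representative route already exist.
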